## **10 Other Evaluations**

### **Additional Safety Evaluation**

Additional safety analysis will be provided by treatment group, by severity, by outcome and related to study drug. Events will be summarized with descriptive statistics (count & percentage).

### **Laboratory Evaluations**

For haematology and biochemistry variables, descriptive summaries of observed values and changes from baseline will be presented by treatment arm. Numerical variables will be described by number of subjects, mean, standard deviation, median, minimum and maximum and categorical variables will be described by number and percentage.

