Itolizumab is an anti-CD6 humanized IgG1 mAb. Itolizumab is an immune modulatory molecule. Itolizumab accumulates in the inflamed lesion. Itolizumab is used in Psoriasis and evaluated in other inflammatory diseases (Rheumatoid Arthritis) with a good safety profile as monotherapy or in combination with other drugs. Itolizumab has a legacy of therapeutic effect after discontinuation of the treatment period. Itolizumab has a potent anti-inflammatory effect reducing the production of pro-inflammatory cytokines IL-6, TNF, IFN γ , IL-17 and IL-1.

Hypothesis:

Itolizumab in COVID-19 patients will control the pro-inflammatory cytokine storm syndrome, by immunomodulation of Teff function and trafficking to the inflammation site, sparing Tregs and preserving the anti-viral response, reducing the morbidity and mortality.

Summary of Clinical Safety with Itolizumab:

Itolizumab Injection has been administered to 338 patients with RA or psoriasis (including those with psoriatic arthritis) for up to 52 weeks in clinical trials till date and has been found to be well tolerated and safe.

Itolizumab Injection (Alzumab™) was launched in India on 10 Aug 2013, as a solution for IV infusion of 1.6 mg/kg once every two weeks for 12 weeks, followed by 1.6 mg/kg every four weeks up to 24 weeks (each 5 mL vial contains 25 mg of itolizumab) for the treatment of patients with active moderate to severe chronic plaque psoriasis who are candidates for systemic therapy.

Post-marketing, periodic safety update reports (PSURs) have been generated and submitted to the licensing authority. Based on these periodic reviews of safety data, the overall safety profile evaluation for Itolizumab Injection has remained unchanged. No new clinically significant issues arose which warranted changes to the current reference safety information (RSI).

The most commonly (occurring in $\geq 5\%$ patients) reported AEs in the Phase 3 study were infusion reactions (which are managed by premedication), pyrexia, upper respiratory tract infections and pruritus. The majority of the events were mild or moderate in severity. There were small transient reductions observed in the mean ALC during the initial infusions; however ALC increased with continued dosing. The small reduction in ALC did not appear to increase the incidence of infection.

Summary of Contraindications/warning:

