**Biochemistry assessments (blood test) include blood urea, liver function tests (i.e. serum bilirubin, AST, ALT, ALP, Serum albumin), Lipid profile (including triglyceride), LDH, serum creatinine, Procalcitonin, d-Dimer, Trop-I, Ferritin. All blood samples for hematology and biochemistry must be collected prior to dosing, and additional as per investigator discretion.

Note: Hematology and Biochemistry including (Procalcitonin, d-Dimer, Trop-I, Ferritin, LDH and CRP) are recommended every 48 to 72 hours.

§: To be recorded daily: TLC; DLC, ANC, ALC; Platelet count; S. creatinine; T. Bilirubin; morning Vitals –pulse, BP, RR; Temperature (highest temperature of the day), PaO₂/FiO₂, MAP, GCS. These daily assessments are mandatory until patient moved out of ICU/equivalent. If patient is not admitted in the ICU/equivalent at the time of enrolment, then it is recommended to capture these assessments daily for first 7 days.

@ Premedication: **In arm A:** Hydrocortisone 100 mg i.v (or equivalent short acting glucocorticoid) and Pheniramine 30 mg per i.v. about 30 \pm 10 minutes prior to infusion.

To be repeated as suggested by the investigator in ICU setting. Earlier chest X ray report may be considered after discussing with sponsor.

d: Cytokine levels in serum: such as IFN- α , TNF- α , IL-17, IL-6, IL-1, IL-4, IL-2, IL-10, GM-CSF, IFN- γ at baseline, before every dose and 12-24 h after dose in Arm A. In Arm B, same panel will be assessed at baseline, 12 to 24 h and approx. 7 and 14 days after randomization. Immunophenotyping in whole blood samples: Teff cells (CD4, CD8, Treg cells), TH17 and macrophage activated cells will be analysed at baseline, 12-24 h after 1st dose and 24h after the second/last dose in Arm A and at baseline, 12-24 h and approx. 7 days after randomization in Arm B.

Timing of administration of Itolizumab:

Patients should be randomized in the trial and given Itolizumab who are in moderate to severe ARDS as defined by PaO₂/Fio₂ ratio of < 200 or more than 25% deterioration from the immediate previous value.

OR

Baseline serum ferritin level \geq 400 ng/mL or IL-6 levels greater than 4 times ULN, if known

Note: Either of Inclusion number 6 or 7 is required for inclusion of the patient into the study. Since there is logistical delay in getting results in time, biomarker data as inclusion criteria may be used if already known.

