Certain: A clinical event, including laboratory test abnormality, occurring in a plausible time relationship to drug administration and which cannot be explained by concurrent disease or other drugs or chemicals. The response to withdrawal of the drug [de-challenge] should be clinically plausible. The event must be definitive pharmacologically or as a logical phenomenon, using a satisfactory re-challenge procedure if necessary.

Probable /Likely: A clinical event, including laboratory test abnormality, with a reasonable time sequence to administration of the drug, unlikely to be attributed to concurrent disease or other drugs or chemicals and which follows a clinically reasonable response on withdrawal [de-challenge]. Re-challenge information is not required to fulfill this information.

Possible: A clinical event, including laboratory test abnormality, with a reasonable time sequence to administration of the drug , but which could also be explained by concurrent disease or other drugs or chemicals. Information on drug withdrawal may be lacking or unclear.

Unlikely: A clinical event, including laboratory test abnormality, with a temporal relationship to drug administration which makes a causal relationship improbable, and in which other drugs, chemicals or underlying disease provide plausible explanations.

Unrelated: Event or laboratory test abnormality – is clearly NOT related to the investigational agent(s)

e. Laboratory Abnormalities

Abnormal laboratory findings (e.g., biochemistry, hematology) or other abnormal assessments (e.g., electrocardiogram, X-rays, vital signs) per se are not reported as AEs. However, abnormal findings that are deemed clinically significant must be recorded as AEs if they meet the definition of an adverse event (and recorded as an SAE if they meet the criteria of being serious) as described previously, as per the classifications accorded in NCI CTCAE v5.0 for laboratory AEs.

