ALZUMAbTM has not been studied in patients with active intercurrent infections, or a past history of serious infections such as HIV-AIDS or tuberculosis [see Contraindications]. ALZUMAbTM has not been studied in the patients having low absolute neutrophil or lymphocyte count (<1500 cell/ μ L). The effect of ALZUMAbTM in these special populations is unknown. Caution should be exercised while administering itolizumab to immunocompromised patients with Human Immunodeficiency Virus (HIV), Hepatitis B, Hepatitis C infection and patients receiving or received chronic steroid therapy.

Prior to initiating ALZUMAbTM administration, patients should be screened for active or latent tuberculosis infection using Mantoux test and or chest x-ray.

Use with other biologics

ALZUMAbTM has not been studied in combination with other biological agents approved for the treatment of plaque psoriasis. ALZUMAbTM should not be used with such agents because of the possibility of increased immunosuppression and increased risk of infection.

Vaccination

No data are available on the response to vaccination with live/attenuated vaccines or on the secondary transmission of infection by live vaccines in patients receiving ALZUMAbTM therapy. Based on its mechanism of action, ALZUMAbTM may blunt the effectiveness of some immunizations. It is recommended that live/attenuated vaccines not be given concurrently with ALZUMAbTM. The patient's vaccination record and the need for immunization prior to receiving ALZUMAbTM should be carefully investigated. The interval between vaccination and initiation of ALZUMAbTM therapy should be in accordance with current vaccination guidelines. Caution is advised in the administration of live vaccines to infants born to female patients treated with ALZUMAbTM during pregnancy, since ALZUMAbTM may cross the placenta.

Malignancies

None of the patients on itolizumab treatment developed malignancies during the clinical trials.

Drug Interactions

Drug interaction studies have not been performed with ALZUMAB™.

Pregnancy and Lactation

Use in Pregnancy

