### **Secondary Efficacy Evaluation**

Biomarkers (IL-6, TNF-a, IL1, IL17, etc...) will be summarize using summary statistics.

Lymphocyte count will be summarized using count & percentage.

PaO2 (partial pressure of oxygen) / FiO2 (fraction of inspired oxygen, FiO2) ratio (or P/F ratio) calculated from arterial blood gas analyses. Radiological response will be summarized in descriptive manner.

Duration of hospitalization will be summarized using descriptive statistics.

Time to independence from non-invasive mechanical ventilation and from oxygen therapy will be summarize using summary statistics.

Biomarkers (IL-6, TNF-a, IL1, IL17, etc...) Lymphocyte count, CRP (C-reactive protein) level, PaO2 (partial pressure of oxygen) / FiO2 (fraction of inspired oxygen, FiO2) ratio (or P/F ratio), will be summarized with descriptive statistics. Change from Baseline will be presented along with 95% CI for the difference between two treatments will be reported.

Radiological response, Duration of hospitalization & Remission of respiratory symptoms will be summarized using descriptive statistics.

Number of participants with treatment-related side effects as assessed by Common Terminology Criteria for Adverse Event (CTCAE) version 5.0 graded according to CTCAE criteria (v5.0) will be summarized based on frequency and proportion of total subjects, by system organ class and preferred term. Proportion of subjects with IRR in both the arm will be presented. An overall summary of deaths will be presented by treatment arms.

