## 15. Supplementary Tables

**Table S1: Mean Lymphocyte count**

	Baseline	Day 2/3	Day 7	Day 14	Day 21	Day 30/EOS
n						
Arm A						
Arm B						

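### No planned table counts patients whose lymphocytes, neutrophils or platelets fall below a stated limit, and the lymphocyte count and percentage promised in SAP 9 has no category

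*SAP*

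**What the plan says.** **Known effect.** Protocol section 3, in the clinical safety summary, states: "There were small transient reductions observed in the mean ALC during the initial infusions; however ALC increased with continued dosing". It adds that infections did not appear to increase. That summary covers rheumatoid arthritis and psoriasis. The package insert (Protocol Appendix 4, Special Warnings, Infections) says the product "has not been studied in the patients having low absolute neutrophil or lymphocyte count", with 1500 cells/µL as the figure.

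**Entry and collection.** Exclusion criteria 12 to 14 set entry limits of ANC 1000, platelets 50,000 and ALC 500 per mm3. The daily-assessment footnote in Protocol 8.1 reads "To be recorded daily: TLC; DLC, ANC, ALC; Platelet count". Daily recording is mandatory until the patient leaves ICU or equivalent. For patients not in ICU at enrolment it is recommended for the first 7 days.

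**Planned summaries.** SAP 10 (Laboratory Evaluations) says "For haematology and biochemistry variables, descriptive summaries of observed values and changes from baseline will be presented by treatment arm", using n, mean, SD, median, minimum and maximum. Shell 14.1.8 applies these at baseline and Days 7, 14, 21 and 30/EOS. The shell titled "Table S1: Mean Lymphocyte count" adds Day 2/3. SAP 9 says "Lymphocyte count will be summarized using count & percentage". A later paragraph of the same section asks for descriptive statistics, and change from baseline with a 95% CI for the treatment difference.

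**Adverse events.** Under Protocol Appendix 3, section e, abnormal laboratory findings "per se are not reported as AEs". Those deemed clinically significant must be recorded if they meet the AE definition. The investigator judges this, and usually a sign or symptom should be present or likely soon.

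**The concern.** The sponsor's own summary places the lymphocyte effect around the initial infusions and describes it through the mean. The relevant safety question here is how many patients reach a very low count, in a population whose eligible range extends below anything the package insert says was studied. Visit summaries starting at Day 7 miss a fall that has recovered by then, and a Day 2/3 mean does not say how many patients were low. The daily values that could answer the question feed no planned table.

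SAP 9 has a defect visible in its own text. A count and percentage needs a category; none is defined and no shell contains one, so the output cannot be programmed as written. Safety is part of the primary objective. Without a prespecified count, the lymphocyte result would rest on averages, or on a cut-off chosen after the data are seen.

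**Working it through.** The documents give no ALC event rate, size of fall or sample size calculation, so there is no planned figure to reproduce. The check compares what is collected with what is tabulated, then asks what the tabulated quantities can reveal.

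**1. Where an early low count could appear**

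| Place | Content | Shows how many patients were low early? |
|---|---|---|
| Shell 14.1.8 | N, mean (SD), median, min, max; baseline, then Day 7 onward | No; nothing between baseline and Day 7 |
| Table S1 | Mean lymphocyte count, including Day 2/3 | No; mean only |
| Figure 3 | Change from baseline, key laboratory parameters including lymphocytes | No count specified |
| SAP 9 | Count and percentage for lymphocytes | Undefined |
| Listing 16.1.9 | Individual pre-dose and 12 h post-dose results with reference limits | By hand, for those samples only |
| TEAE tables | Findings judged clinically significant | Only those recorded as AEs |

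Listing 16.1.9 has no column for daily values, and Arm B has no dose to anchor its result columns. For ANC and platelets no Day 2/3 summary table is planned.

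**2. A mean change does not fix the count.** Constructed values: 20 patients, all starting at ALC 900.
- All fall by 100: mean change = -100; number below 500 = 0.
- Four fall by 500 and sixteen do not change: mean change = -(4 × 500)/20 = -100; number below 500 = 4 of 20 (20%). The median stays at 900 and the minimum is 400.

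The minimum would show that at least one patient was below 500 at that visit, but not how many. It is not shown at Day 2/3.

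**3. Nor does the mean itself.** Assume ALC is lognormal with mean m and coefficient of variation CV. Then s² = ln(1 + CV²), μ = ln(m) - s²/2, and the share below 500 is Φ[(ln 500 - μ)/s].
- m = 900: 3.2% with CV 30%, 15.7% with CV 50%. In 20 patients: 0.6 against 3.1.
- m = 1200: 0.2% with CV 30%, 5.3% with CV 50%.

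The means and CVs are assumptions. Table S1 gives no SD, so it could not separate these cases.

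**4. What a count could show at the planned size.** About 30 patients at 2:1 gives 20 in Arm A and 10 in Arm B. Exact (Clopper-Pearson) 95% intervals:
- 0/20: 0 to 16.8%; 1/20: 0.1 to 24.9%; 4/20: 5.7 to 43.7%.
- 0/10: 0 to 30.8%; 1/10: 0.3 to 44.5%.

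The chance of seeing at least one case is 1 - (1 - p)^n, for an assumed true rate p:
- p = 5%: 64% in Arm A, 40% in Arm B.
- p = 10%: 88% and 65%.
- p = 20%: 99% and 89%.

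The count is feasible, but it is descriptive only.

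**The case against.** A reader might infer that the SAP reports lymphocytes solely as averages, that low patients go uncounted altogether, and that the drug would be pushing them under a safety threshold. The documents do not support this:
- SD, median, minimum and maximum are planned from Day 7.
- Listing 16.1.9 shows individual values, and with about 20 patients in Arm A low results near an infusion could be counted by hand.
- Clinically significant findings must be recorded as AEs and would reach the TEAE tables.
- ALC below 500 is an entry exclusion. No on-treatment limit is set, and withdrawal for laboratory abnormalities is by investigator opinion.
- The reported fall was small and transient, with no apparent rise in infections. The package insert reports no clinically meaningful between-arm differences in haematology abnormalities in the phase 3 psoriasis study. The Protocol background attributes cytopenia to COVID-19 itself, so a low count is not evidence of a drug effect.

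It can also be said that a large early fall would move the Day 2/3 mean in Table S1, that SAP 6 and 13 allow extra tables, and that a lowest-value count is distorted by unequal sampling.

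All of this limits the point without removing it. An asymptomatic low value need not become an AE, and in an open-label trial that judgement may differ by arm. The listing is not a between-arm summary. Because the disease itself lowers counts, a comparison by arm is what is needed. Permission to add tables is not prespecification. The sampling objection is valid and shapes the fix.

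**Conclusion.** The concern holds as a reporting gap. Blood counts are recorded daily for at least part of the stay, but the number of patients with an early low value reaches no planned between-arm summary, and SAP 9 promises a lymphocyte count and percentage that it does not define.

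No planned estimate or test is invalidated, and the data are already collected. The size of what could be missed is unknown because the documents give neither the fall nor its spread. Under the assumed distributions, the share below 500 at one time point ranges from 0.2% to 15.7%, and in the constructed example 0 and 4 of 20 give the same mean change. These figures show that the count cannot be recovered from the mean; they do not show that patients will fall that low, or that itolizumab would be the cause. Whether the entry limits are appropriate is a clinical matter and is not judged here. The change should be made: safety is a primary objective and the cost is small.

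**What to change.** In SAP 10 and section 14.1.8, add one descriptive table on the safety population, by arm, using all recorded values without the ±2-day substitution in SAP 12:
- (a) the lowest post-baseline ALC, ANC and platelet count per patient, over Days 1-7 and Days 1-30;
- (b) the number and percentage of patients below the entry limits (ALC <500, ANC <1000, platelets <50,000/mm3), with exact 95% CIs. State that these are reporting cut-offs only and set no rule for treatment;
- (c) the worst CTCAE v5.0 laboratory grade against the baseline grade.

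Show the number of sampling days per arm beside the table, and repeat (b) on the visits common to both arms. In SAP 9, point the lymphocyte count and percentage to this table.

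**Cost.** One extra table and its programming, from data already collected. The downside is that patients sampled more often have more chances of a low value. Sampling intensity varies with ICU stay and with the dose-linked samples in Arm A. Showing sampling days discloses this bias but does not remove it; the common-visit repeat reduces it, at the price of missing falls between visits. At about 20 against 10 patients the intervals will be wide, so the table should be read descriptively.

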### **Vital Signs and Physical examination**

Descriptive statistics of each vital signs parameter will be presented for the Safety Population, showing the observed visit and change from baseline to each visit value. These summaries statistics (N, mean, SD, median and Min, Max) will be presented by visit for each treatment arm

## **11 Interim Study Report**

Data will be provided to DSMB (constituted prior to first patient screened) on a periodic basis. Based on DSMB recommendation, interim clinical study report may be prepared and submitted to DCGI/regulatory agencies.

## **12 Key Definitions**

For few assessments (weight, physical examination, vital signs haematology, biochemistry Chest X Ray/CT scan), screening assessments will be considered as baseline assessment (as day 1).

Stable SpO2:

- Stable SpO2: Defined as absence of increase in FiO2 to maintain Spo2 ≥ 92%
- Improvement of SpO2: Defined as decrease in FiO2 to maintain SpO2 >92%

Stable PaO2:

- Stable PaO2: Defined as up to 10% change in PaO2/FiO2 ratio from baseline
- Improvement of PaO2: Defined as > 10% improvement in PaO2/FiO2 ratio from baseline (including patients weaned off oxygen)

If assessment is missing on particular day then it should be captured from assessment available in next two days.

For lab parameters, if assessment is missing on particular day, then it should be captured from assessment available in ± 2 days.

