ALZUMAB™ should not be administered to patients having history of severe allergy or known hypersensitivity reaction to any component of ALZUMAB™ or any murine proteins. Additionally, ALZUMAB™ is contraindicated in patients with any active serious infection including tuberculosis and HIV-AIDS.

It is recommended that live/attenuated vaccines not be given concurrently with ALZUMAB™.

As with other IgG antibodies, itolizumab may cross the placenta during pregnancy. The available clinical experience is too limited to exclude a risk, and administration of ALZUMAB™ is therefore not recommended during pregnancy.

Infections and Reactivation of Tuberculosis

Physicians should exercise caution before and during Itolizumab Injection treatment in patients with a history of recurrent infections or underlying conditions which may predispose them to serious infections. Patients should be monitored closely for the development of signs and symptoms of infection during and after treatment with Itolizumab.

4. Objectives

Primary Objectives:

To study the efficacy and safety of adding Itolizumab in patients with Moderate to Severe COVID-19 complications (Cytokine Release Syndrome).

Secondary Objectives:

To study the effect of immunomodulation by Itolizumab and its correlation to clinical improvement by evaluating biomarker data (IL6, TNF-a, IL17, IL1, Interferon -A etc.) before and after Itolizumab treatment

5. Outcome Measures

Primary Outcome Measures:

1. Proportion of patients with deterioration of lung function as measured by*:
 - Stable SpO₂ without increasing FiO₂
 - Stable PaO₂ without increasing FiO₂
2. Reduction of endo-tracheal intubation rate, measured as rate of patients needing intubation*
3. Reduction in proportion of patients who need*
 - Non-invasive ventilation
 - Invasive mechanical ventilation
 - High flow nasal oxygen
4. Time of duration of mechanical ventilation or time to end of mechanical, measured as elapsed time from the start date of mechanical ventilation to the weaning date, for patients needing intubation*
5. One-month mortality rate between the two arms* [Time Frame: up to 1 month]

1-month mortality is defined as the ratio of patients who will live after 1month from study start out of those registered at baseline

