## 3.2 Outcome Measures

### 3.2.1 Primary endpoint

1. Proportion of patients with deterioration of lung function as measured by\*:
  - Stable SpO2 without increasing FiO2
  - Stable PaO2 without increasing FiO2
2. Reduction of endo-tracheal intubation rate, measured as rate of patients needing intubation\*
3. Reduction in proportion of patients who need\*
  - Non-invasive ventilation
  - Invasive mechanical ventilation
  - High flow nasal oxygen
4. Time of duration of mechanical ventilation or time to end of mechanical, measured as elapsed time from the start date of mechanical ventilation to the weaning date, for patients needing intubation\*
5. One-month mortality rate between the two arms\* [ Time Frame: up to 1 month ] 1-month mortality is defined as the ratio of patients who will live after 1 month from study start out of those registered at baseline
6. Change in inflammatory markers like CRP (C-reactive protein) level, d-Dimer, ferritin etc. [ Time Frame: Arm A; baseline, during treatment (Before every dose and 12 to 24 h after every dose) up to 1 month, Arm B: baseline, 12 to 24 h and approx. 7 and 14 days after randomization ]

\* Applicable for both the arm

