### **13 Programming Considerations, Listing of Tables, Figures & Format, Software detail**

All tables, data listings, figures (TLFs), and statistical analyses will be generated using SAS® for Windows, Release 9.4 (SAS® Institute Inc., Cary, NC, USA) or any other validated statistical software. One SAS program will be used to create several outputs / a separate SAS program will be created for each output. Output files will be delivered in Word / pdf format.

For few assessments (weight, physical examination, vital signs haematology, biochemistry Chest X Ray/CT scan), screening assessments will be considered as baseline assessment (as day 1).

Missing data:

All attempts will be made to collect all data per protocol. Any data point that appears to be erroneous or inexplicable based on clinical judgment will be investigated as a possible outlier. If data points are identified as outliers, sensitivity analyses may be performed to examine the impact of including or excluding the outliers. Subjects who meet fatal outcome during the observing period up to 30 days will be an event. Subjects lost to follow up or withdraw consent during the observing period, will be censored at last assessment. Patient data will be censored at the time of their last observed assessment in case of lost to follow up, withdrawal consent or after 30 days of enrolment.

Following Rules may be applied for the derivation of efficacy endpoints

- Patients who discharged from hospital (with improvement, Off O2), the status at discharge will be carried forward.
- Patients who lost to follow up will be considered as Non evaluable (NE)
- Patients who worsen or met fatal outcome, status at event will be carried forward.

Note: Telephonic improvement of weaning of O2 will be considered as improved.

These rules will be applied to analyse following endpoint:

Proportion of patients with deterioration of lung function as measured by:

- Stable SpO2 without increasing FiO2
- Stable PaO2 without increasing FiO2

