## 14.2 Primary outcome measures

### 14.2.1 Primary Outcome Measures

Visit*		Arm A (N=XX)	Arm B (N=XX)
Baseline	patients with Stable SpO2 without increasing FiO2	XX (XX.X %)	XX (XX.X %)
	patients with Stable PaO2 without increasing FiO2	XX (XX.X %)	XX (XX.X %)

\*day 7, day 14, day 21 and day 30/EOS or all available visits

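### SAP 12 defines stable and improved PaO2 by the PaO2/FiO2 ratio alone, so the bar on raised FiO2 in primary endpoint 1 can be coded in or left out

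*SAP*

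**What the plan says.** Protocol section 5 words the PaO2 component of primary outcome 1 as "Stable PaO₂ without increasing FiO₂". SAP 3.2.1 repeats it, as do SAP 9 and the derivation rules in SAP 13. The row to be counted in table shell 14.2.1 is "patients with Stable PaO2 without increasing FiO2". In all these places the FiO2 condition is part of the endpoint.

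SAP 12 (Key Definitions) supplies the working rules:

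- Stable PaO2: "Defined as up to 10% change in PaO 2 /FiO 2 ratio from baseline".
- Improvement of PaO2: "Defined as > 10% improvement in PaO 2 /FiO 2 ratio from baseline (including patients weaned off oxygen" (the parenthesis closes after this phrase).
- Stable SpO2, for comparison: "Defined as absence of increase in FiO 2 to maintain Spo 2 ≥ 92" (per cent).

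The SpO2 line makes an FiO2 increase part of the definition. The two PaO2 lines use only the ratio.

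SAP 9 provides for a between-arm difference in proportions with a 95% confidence interval, and possibly a p-value, for this endpoint. Among the primary endpoints, only one-month mortality is treated in the same way.

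**The concern.** SAP 12 is the only place where the PaO2 component is turned into something a programmer can code, and what it gives does not enforce the endpoint's own condition. A ratio is blind to a joint change in numerator and denominator: if FiO2 is raised and PaO2 follows in proportion, the ratio does not move.

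The two halves of the endpoint are also built differently. For SpO2, the key definition carries the FiO2 condition even though the SpO2 row label states it too. A programmer who takes SAP 12 as complete for SpO2 would reasonably take it as complete for PaO2, and would code the ratio alone. Another programmer could read the PaO2 row label as adding a second test. The SAP does not say which is meant, and for the PaO2 component it gives no time point against which an FiO2 increase is judged.

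At stake is an endpoint with a planned between-arm comparison in an open-label trial of about 30 patients. If the rule is left open, the choice between two defensible codings could be made with the results in view.

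**Working it through.** The plan states no figure for this point and has no formal sample size calculation, so there is nothing to reproduce. The check is whether the two readings classify the same patient differently.

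**Inputs**

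- Stable: change in ratio within ±10%. Improved: change above +10% (SAP 12). The stable line gives no direction, so both directions are allowed here.
- About 30 patients randomised 2:1 (SAP 4.5).
- Illustrative gas values (assumption, not in the documents): baseline PaO2 60 mmHg on FiO2 0.40. The ratio is 60/0.40 = 150, below the limit of 200 in inclusion criterion 6.

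**Formula**

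Change = (PaO2 later / FiO2 later) ÷ (PaO2 baseline / FiO2 baseline) − 1.

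**Classification from the assumed baseline of 150**

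| Later FiO2 | Later PaO2 | Ratio | Change | SAP 12 alone | SAP 12 plus no FiO2 increase |
|---|---|---|---|---|---|
| 0.44 | 60 | 136.4 | −9.1% | stable | not counted |
| 0.50 | 60 | 120.0 | −20.0% | not stable | not counted |
| 0.60 | 82 | 136.7 | −8.9% | stable | not counted |
| 0.60 | 90 | 150.0 | 0% | stable | not counted |
| 0.60 | 105 | 175.0 | +16.7% | improved | not counted |

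The readings differ in four of the five cases. The second case fails under both.

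**How far the ratio protects by itself**

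Let k = later FiO2 / baseline FiO2. The patient is stable on the ratio when later PaO2 lies between 0.9k and 1.1k times baseline PaO2, and improved above 1.1k.

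- PaO2 unchanged: stable requires 1/k ≥ 0.9, so k ≤ 1/0.9 = 1.111. A relative FiO2 rise above 11.1% fails.
- FiO2 0.40 to 0.60: k = 1.5. Stable requires PaO2 between 0.9 × 1.5 = 1.35 and 1.1 × 1.5 = 1.65 times baseline, that is 81 to 99 mmHg from 60. Above 99 the patient is improved.
- FiO2 0.40 to 0.60 with PaO2 held at 60: the ratio is 60/0.60 = 100, a fall of 33.3%, and the patient fails.

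The readings therefore part when FiO2 is raised only slightly, or when PaO2 rises roughly in step with FiO2 or more.

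**Weight of one patient**

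30 × 2/3 = 20 in Arm A and 30 × 1/3 = 10 in Arm B. One reclassified patient moves the proportion by 1/20 = 5 points in Arm A or 1/10 = 10 points in Arm B.

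**The case against.** The best defence is that the condition is still in the plan. It is in the endpoint list, the analysis text, the derivation rules and the row label that is counted. SAP 12 can be read as defining only the term stable PaO2, with the label adding the second test; on that reading a patient on raised FiO2 is not counted. This stands as far as it goes. A reader might infer that the SAP has removed the condition from the endpoint, or that such patients will be scored as successes. The documents do not support either: they leave two readings, and the consequence depends on which is coded.

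The ratio also penalises many FiO2 increases, as shown above, and it is arguable whether an unchanged ratio on more oxygen is a deterioration of lung function. But the endpoint as worded excludes an FiO2 increase, and the ratio does not enforce that.

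Three further inferences should be resisted.

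- That the two halves of the endpoint would contradict each other for the illustrated patient. The SpO2 rule concerns FiO2 raised to keep SpO2 at 92% or above, and the example contains no SpO2 value.
- That patients on raised FiO2 will be reported as improved. Shell 14.2.1 has only stable rows. SAP 13 does use improved as a status for this endpoint ("Telephonic improvement of weaning of O2 will be considered as improved"), but nowhere says how improved patients enter the table. That is a gap of its own, and the fix should close it.
- That some share of each arm is misclassified. The documents give no basis for any percentage.

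Mean FiO2 and mean ratio are tabulated by arm and visit (Tables S2 and S5), so a general rise in FiO2 would be visible. That does not settle how an individual patient is classified.

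**Conclusion.** The point holds as an ambiguity in the working definition of a primary endpoint. SAP 12 defines stable and improved PaO2 by the ratio alone, while the endpoint and its table row also require that FiO2 has not been increased. The two resulting codings classify some patients on raised FiO2 differently, and coding SAP 12 alone contradicts the endpoint's wording.

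The size is known only per patient: about 5 points in Arm A or 10 in Arm B, assuming 30 patients split 20 to 10. The number of patients affected, and the direction of any effect on the between-arm difference, cannot be derived from the documents. The gas values are illustrative and show only that the readings can differ. No sample size, power or alpha figure changes. The rule should be settled before database lock because this endpoint has a planned between-arm comparison in a small open-label trial.

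**What to change.** In SAP 12:

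1. Add to both the stable PaO2 line and the improvement line: *and FiO2 not higher than at baseline (baseline as defined in SAP 8)*. A patient whose FiO2 is above baseline is then not counted as stable or improved in table 14.2.1.
2. State that the 10% limit for stable concerns worsening of the ratio.
3. State that improved patients, including those off oxygen, count as not deteriorated, so that their place in table 14.2.1 is clear.

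The cost is a few lines of SAP text and one programming condition. FiO2 is already collected and reported (table 14.1.7, Table S5, Listing 16.1.7), and SAP 1 allows revisions before database lock with reasons given in the study report. The downside is that the reported success rate may be slightly lower, because the 10% tolerance no longer admits a small FiO2 increase. The change concerns outcome classification only and alters no clinical rule.
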